#### B. Determination of Subject s/Data for Analysis

The analysis will be conducted using the modified intent-to-treat (mITT) set.

### 3.2.1.4 Sample Size Methods and Assumptions

[figure not shown]
Sample size was estimated using SAS v9.2 Proc Power. The sample size was calculated under an asymptotic z-test for a single binomial proportion with continuity adjustment under the following assumptions:

Power = 90%, Significance level = 0.025 (one-sided), Assumed underlying effectiveness rate = 55%, Performance goal = 45%.

Long-term (> 12 months) effectiveness of pulmonary vein isolation for treatment of atrial fibrillation (AF) ranges from 44-70%, with 40% reported as the minimum goal by physicians. Shah et al reported that the annual rate of atrial fibrillation recurrence after one year was 8.8% and Zou et al reported a similar annual rate of 7%. Based on the STOP AF results and assuming an annual rate of atrial fibrillation recurrence of 7%, the estimated effectiveness rate at 36 months would be approximately 55%. The performance goal of 45% was determined from the lower bound of 95% CI for the primary effectiveness rate in STOP AF study.

Figure 2 presents the sample size at different primary effectiveness rates under the assumptions outlined above.

**Figure 2. Sample Size vs. Primary Effectiveness Rate**

If the underlying effectiveness rate is assumed 55%, a total of 270 evaluable subjects will be required to provide 90% power to meet this effectiveness objective.

### 3.2.2 Primary Objective #2 (Primary Safety Objective)

The primary safety endpoint is the rate of subjects experiencing one or more Cryoablation Procedure Events (CPE) through 12 months.

#### 3.2.2.1 Hypothesis

If the upper bound of the confidence interval for CPE rate at 12 months is less than the performance goal of 14.8%, we can conclude the primary safety objective is met.

The following hypothesis will be tested in a one-sided test at the 0.025 significance level.:

Ho: Ps ≥ 14.8%

Ha: Ps < 14.8%

where Ps is the probability of subjects with one or more CPEs and 14.8% is the pre-specified performance goal based on the upper bound of 95% CI for the primary safety rate in the STOP AF study.

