## 2 RATIONALE FOR STUDY DESIGN

### 2.1 Study Purpose

The pivotal trial (STOP -AF) of the Arctic Front® Cardiac Cryoablation Catheter System with the adjunctive use of the Freezor® MAX Cardiac Cryoablation Catheter to electrically isolate pulmonary veins (PV) in patients with paroxysmal atrial fibrillation (PAF), compared to a randomized drug control group has been performed and a final report submitted to the FDA resulting in product approval December 2010. A Continued Access Protocol trial (CAPAF) was also conducted to allow collection of additional safety data following modifications implemented into the Arctic Front® Catheter and Cryoablation System. As part of the continued clinical development of the Arctic Front® Cardiac Cryoablation Catheter System, this Post Approval Study (PAS) is being conducted to provide long-term safety and effectiveness monitoring/data per the Pre-Market Approval order (P100010) by the Food and Drug Administration (FDA).

This PAS is a prospective multicenter, non-randomized, single arm, controlled, unblinded clinical study of up to 400 enrolled subjects with PAF who have failed one or more Atrial Fibrillation Drugs (AFDs). All study subjects will be receiving cryoablation with the study devices and, optionally (post-procedure), an Atrial Fibrillation Drug.

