### 3.2.2.4 Sample Size Methods and Assumptions

Sample size was estimated using SAS v9.2 Proc Power. The sample size was calculated under an asymptotic z-test for a single binomial proportion with a continuity adjustment under the following assumptions:  
Power = 90%, Significance level = 0.025 (one-sided), Assumed underlying primary safety event rate = 6%, Performance goal = 14.8%.

The performance goal of 14.8% is selected based on the same assumption defined in version 1.7 of the STOP AF Clinical Investigation plan (January, 2008): "Based on a review of SSEDs for similar types of ablation trials, the expected rate for CPEs in a well-monitored trial of left atrial RF ablation for AF was estimated to be 10% (corresponding to a CPE-free rate of 90%). If 16 of 160 subjects were observed to have at least one CPEs then the resulting one-sided 95% upper confidence bound would be 14.8%."; where SSED is an abbreviation for Summary of Safety and Effectiveness Data.

Figure 3 presents the sample size at different primary safety event rates under the assumptions outlined above.

Figure 3. Sample Size vs. Primary Safety Event Rate

If the underlying safety event rate is assumed 6%, a total of 141 evaluable/mITT subjects will be required to provide 90% power to meet this safety objective.

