## 4 APPENDIX

### 4.1 Overall Sample Size

In order to adequately power for both the primary effectiveness and safety hypotheses, we require a sample size of 270 evaluable subjects to complete 36 months of follow-up. We estimate that the attrition rate will be approximately 10% per year for the duration of the originally intended 5 year follow-up period. Therefore, the final sample size required to achieve 270 subjects followed for 36 months and account for attrition (i.e. 10% per year) is 370 mITT subjects with procedure attempts. It is expected up to 400 subjects will need to be enrolled to ensure 370 mITT subjects with procedure attempts assuming a small number of subjects who are enrolled will not undergo a procedure.

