**5 VERSION HISTORY**

Version	Summary of Changes	Author(s)/Title
1.0	
 
Not Applicable, New Document
 
	[name]
2.0	
 
Replaced assessments scheduled to take place at 5 years to reflect new 3 year timeline of the study replaced 5-year outcomes with equivalent 3-year outcomes.
 
Modified the statistical methods for center pooling to accommodate 20- 30 sites (replaced chi square test with Cochran's Q).
 
Specified details about conducting the tipping point analysis
 
Removed language pertaining to describing subject screening
 
Removed additional objectives 1 and 2, which centered around comparing results between this study and the STOP AF Pivotal study, and are now considered out of scope.
 
Specified an additional analysis describing SF-12 scores at baseline, six months, and at year 1, 2, and 3
 
	[name]

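### Does it matter that the SAP gives two different origins for its 14.8% safety goal?

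*SAP*

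**What the plan says.** The primary safety endpoint is the proportion of subjects with at least one cryoablation procedure event (CPE) through 12 months, tested against 14.8% at one-sided 0.025 in the modified intent-to-treat (mITT) set. The decision rule in SAP 3.2.2.1 starts "If the upper bound of the confidence interval for CPE rate at 12 months is less than the performance goal of 14.8" (per cent); if that holds, the objective is met.

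The SAP states the origin of the goal twice:

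- Section 3.2.2.1: "14.8% is the pre-specified performance goal based on the upper bound of 95% CI for the primary safety rate in the STOP AF study".
- Section 3.2.2.4: the goal rests on "the same assumption defined in version 1.7 of the STOP AF Clinical Investigation plan (January, 2008"). That assumption is a 10% CPE rate expected for left atrial RF ablation, taken from a review of regulatory summaries, followed by a conditional: "If 16 of 160 subjects were observed to have at least one CPEs then the resulting one-sided 95% upper confidence bound would be 14.8" (per cent).

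Three other statements bear on the point. Section 2.1 says the pivotal trial "has been performed and a final report submitted to the FDA resulting in product approval December 2010", so the January 2008 plan is older than the final report. Section 3.2.2.4 sizes the study on "Assumed underlying primary safety event rate = 6" (per cent), and section 4.1 says the final sample size "is 370 mITT subjects with procedure attempts". The version history records for version 2.0: "Removed additional objectives 1 and 2, which centered around comparing results between this study and the STOP AF Pivotal study", as now out of scope.

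**The concern.** The study has a single arm, so the performance goal is the only comparator in the safety test, and its source affects how a met goal can be described. Section 3.2.2.1 describes the safety goal in the same form that 3.2.1.1 uses for the effectiveness goal. For effectiveness, the sample size section repeats the STOP AF origin. For safety, it gives a different one. A reader of 3.2.2.1 alone would take 14.8% as a limit computed from observed STOP AF safety data. On the working in 3.2.2.4, it is a ceiling built on an RF-ablation planning assumption.

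The label is doubtful in a second way. The figure is called a bound of a 95% confidence interval, but the derivation uses a one-sided 95% bound, which is lower than the upper limit of a two-sided 95% interval.

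What seems to be at stake is interpretation. An observed rate clearly above the planned 6%, or even at the 10% RF figure, could still meet the goal, and a report relying on 3.2.2.1 might then present it as falling below a STOP AF confidence limit. Version 2.0 also dropped the separate comparisons with STOP AF, so this clause is the only remaining text linking the safety conclusion to STOP AF results.

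**Working it through.** **1. Does 14.8% follow from 16/160?** Inputs from 3.2.2.4: x = 16, n = 160, so 16/160 = 10.0%. The exact (Clopper-Pearson) upper bound at confidence c is the c-quantile of Beta(x + 1, n − x) = Beta(17, 144).

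- c = 0.95 (one-sided 95%): 14.79%, which rounds to the stated 14.8%.
- c = 0.975 (upper limit of a two-sided 95% interval): 15.73%.

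The derivation in 3.2.2.4 therefore reproduces. The wording in 3.2.2.1 cannot be tested directly, because the SAP reports no observed STOP AF safety rate or interval.

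**2. Does the stated sample size rest on 14.8%?** Inputs from 3.2.2.4: p0 = 0.148, p1 = 0.06, one-sided 0.025, power 90%, z-test with continuity adjustment. Power is Φ{[(p0 − p1) − 1/(2n) − 1.96·√(p0(1 − p0)/n)] / √(p1(1 − p1)/n)}.

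At n = 141:

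- √(0.148 × 0.852/141) = 0.02990
- √(0.06 × 0.94/141) = 0.02000
- 1/(2 × 141) = 0.00355
- (0.088 − 0.00355 − 1.96 × 0.02990)/0.02000 = 1.292, so power = 90.2%

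At n = 140 the power is 89.9%, so 141 is the smallest adequate number, as stated. Only the value 14.8% enters, not its source.

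**3. Which results meet the goal?** Take 370 mITT subjects (section 4.1) and, for simplicity, no censoring. With k events, S = 1 − k/370, se = √(k/(370(370 − k)))/|ln S|, and the log-log 95% limits for the event rate are 1 − S^exp(∓1.96·se).

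| k | Rate | 95% limits | Goal |
|---|---|---|---|
| 32 | 8.6% | 6.20–12.01% | met |
| 37 | 10.0% | 7.35–13.54% | met |
| 41 | 11.1% | 8.28–14.75% | met |
| 42 | 11.4% | 8.52–15.05% | not met |

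For k = 41: S = 0.8892, |ln S| = 0.1174, se = 0.01835/0.1174 = 0.1563.

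From 32 to 41 events, then, the goal is met while the whole interval lies above 6%. The binomial probability of landing there is 2.5% if the true rate is 6%, 33% at 8%, 55% at 9% and 61% at 10%. At a true 6%, a passing result of 37 to 41 events has a probability of about 0.2%.

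**4. Does the origin of the goal move any of this?** No. The inputs to step 3 are 370, the interval method and 14.8%. The 32–41 range exists because 14.8% is well above 6%. It is identical under either account of the source and would be the same after any rewording.

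**The case for a change.** The strongest case for a change is that this is the only comparator in a single-arm post-approval study ordered by the regulator, and that the hypothesis section is what a final report would naturally quote. Rewording one clause costs almost nothing. A descriptive row setting the observed CPE rate beside the 6% planning rate and the observed STOP AF rate would guard against over-reading a met goal.

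Part of this stands. The two passages do disagree, the disagreement does not come from redaction or a missing figure, and 3.2.2.1 would be clearer if it matched 3.2.2.4 and said that the bound is one-sided 95%.

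The rest does not carry a change:

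- The SAP nowhere says a met goal will be reported as lying below a STOP AF limit. Section 3.2.2.1 concludes only that the objective is met. The harm is a guess about later wording.
- The Kaplan-Meier CPE rate with its 95% log-log interval is already planned in 3.2.2.3, and the 6% planning rate is already in 3.2.2.4. A reader can put them side by side.
- Showing the STOP AF rate needs a figure that the SAP does not contain, and it would bring back part of a comparison that version 2.0 took out of scope.
- It is not certain which passage is wrong. The reproduced arithmetic favours 3.2.2.4, but 3.2.2.1 may be shorthand for a goal inherited from the STOP AF plan.

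**Conclusion.** The inconsistency is real but clerical. Section 3.2.2.4, where the goal is justified, gives a complete derivation that reproduces to 14.79%, so an analyst or report writer can see where 14.8% comes from. Under either origin the threshold is 14.8%, the level is one-sided 0.025 and the required number is 141. With 370 subjects the last passing count is 41. The effect on any planned result is nil, and no change to the plan is needed.

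The counts assume 370 subjects with no censoring at 12 months. Censoring would shift them, but equally under both accounts. That 3.2.2.1 is the mis-worded passage is the likelier reading and is not proven, since the observed STOP AF safety interval is not in the SAP. The conclusion does not depend on which passage is right.

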### 3.2.2.2 Endpoint Definition

A CPE is a device-related or procedure-related serious adverse event (SAE) with onset between the time of the subject's entry into the procedure room for the study-specified cryoablation procedure (Day 0) through the indicated onset intervals as set out in the following Table 1:

**Table 1: Cryoablation Procedure Events**

Cryoablation Procedure Events (CPEs)	Onset Interval
Access site complications requiring: Transfusion of 3 or more units or Surgical intervention or Permanent loss or functional impairment	Through 7 days
Cardiac damage (including MI) except for Pulmonary vein stenosis*	Through 7 days
Atrio-esophageal fistula	Through 12-months
Embolic complications (including stroke)	Through 12-months
Arrhythmias	Through 7 days
Persistent phrenic nerve palsy*	Through 7 days
Death	Through 12-months
	Through 7 days

\* CPE will be assessed at the completion of the follow-up visit, as determined by CT/MRI Core Lab.

\*\* CPE will be assessed at the completion of the follow-up as determined by chest X-ray (insp/exp)

- Pulmonary vein stenosis is defined as > 75% reduction in the baseline area after 6-month follow-up.

- Phrenic nerve palsy (alternatively, Phrenic Nerve Injury or PNI) is defined as abnormal diaphragm excursion as demonstrated during the post-cryoablation procedure fluoroscopy. PNI events are considered persistent if they are unresolved at 12 months.

CPEs exclude

1. Adverse events that are normal and expected concomitants of catheterization and diagnostic and ablation electrophysiology (EP) procedures, such as induced arrhythmia and groin ecchymosis, but only IF that AE resolves completely AND involves only routine responses such as medication, fluids, compression, temporary pacing, or cardioversion.
2. Atrial fibrillation or atrial flutter occurring during post-procedural hospitalization.

- CPEs will be accrued for Retreated Subjects for the comparable 7 day period following a repeat cryoablation.

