#### 3.1.4.2 Missing Data

The impact of missing data on the analysis of primary effectiveness and safety objectives is expected to be small since the Kaplan-Meier method will be performed for the primary objectives. For subjects who are lost to follow-up, the time to event will be censored at the last contact date.

Analysis will be based on available cases. The reasons for study withdrawal will be documented. There are no plans for imputation of any missing data. However, we will compare differences in baseline characteristics between subjects with complete data and subjects with early exit. Also, if the primary objectives are met ( $p < 0.05$ ) at 3 years, with >

5 subjects exiting prior to the 3-year follow-up, a tipping point analysis will be conducted to assess sensitivity to missing data. Missing data is defined here as subjects with less than 3 years of followup.

Data will be sorted by ascending event times, and subjects who are censored prior to the 3-year visit are assigned an event time equal to the date of last contact (index ablation date). Then, for each observation:

- 1) If the observation is censored, set time = time + 1 and event = 1.
- 2) Apply the logrank test (specified in section 3.2.1 or 3.2.2 for efficacy and safety, respectively) to find the new two-sided p-value and 95% loglog confidence interval.

The first observation where the confidence interval includes the performance goal (and the corresponding p-value  $\geq 0.05$ ) is the tipping point for the primary safety analysis. For either primary endpoint, if fewer than 5 subjects have missing data, a worst case analysis will be done instead of a tipping point analysis. This analysis will be performed in the mITT dataset.

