### 3.2.2.3 Analysis Methods

#### A. Statistical Methodology

The Kaplan-Meier method will be used to estimate the probability of a subject experiencing one or more CPE at 12 months follow-up. The standard error will be approximated using Greenwood's formula. A two-sided 95% log-log confidence interval for the probability will be constructed. The Kaplan-Meier estimate and its 95% log-log confidence interval will be constructed from the day of study specified cryoablation procedure (Day 0) through the end of follow-up. For subjects with safety events, the days of follow-up will be computed as the days from Day 0 to the onset date of the first safety event. For subjects without safety events, days of follow-up will be computed as the days from Day 0 through the last follow-up. For subjects who are lost to follow-up, the last contact date will be used as the last follow-up date.

The 12 month visit may occur after 365 days since the visit window runs until 30 days past day 365. Not including events that result from assessment at a 12 month visit, but after day 365 could underestimate the proportion at 1 year due to 12 month visits that occur after 365 days. This potential bias is addressed in the statistical analysis by considering the date of recurrence to be exactly 12 months (365 days) from the study ablation procedure so that these events will be counted as SPE in the 12-month Kaplan-Meier analysis.

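### As written, phrenic nerve palsy still unresolved at an exit before month 12 is censored without an event, so the primary safety rate is biased slightly downward

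*SAP*

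**What the plan says.** - **Definition (SAP 3.2.2.2, Table 1 notes).** PNI is identified as "abnormal diaphragm excursion as demonstrated during the post-cryoablation procedure fluoroscopy", so its onset is at or near Day 0. Whether it counts is settled later: "PNI events are considered persistent if they are unresolved at 12 months".
- **Event time (SAP 3.2.2.3 A).** For subjects with an event, "the days of follow-up will be computed as the days from Day 0 to the onset date of the first safety event".
- **Late visits (SAP 3.2.2.3 A).** Events that come from a 12-month visit held after day 365 are handled by "considering the date of recurrence to be exactly 12 months (365 days) from the study ablation procedure". Nothing is said about subjects who have no 12-month visit.
- **Loss to follow-up (SAP 3.1.4.2).** "For subjects who are lost to follow-up, the time to event will be censored at the last contact date". Also: "There are no plans for imputation of any missing data". The section expects missing data to matter little because Kaplan-Meier is used.
- **Sensitivity analysis (SAP 3.1.4.2).** A tipping-point analysis, or a worst-case analysis when few data are missing, turns censored subjects into events. Missing data are defined there by 3 years of follow-up.
- **Adjudication (SAP 3.1.2).** The adjudication committee determines CPE status and onset date. No convention is given for a palsy whose 12-month status is unknown.
- **Attrition (SAP 4.1).** "We estimate that the attrition rate will be approximately 10% per year".

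**The concern.** Censoring works in a Kaplan-Meier analysis when a censored subject's possible event lies after the censoring time. The subjects still under observation then stand in for the one who left. Here the order is reversed. The event, if there is one, sits at about Day 0, but whether it exists is learned only at month 12. A subject lost at month 6 with palsy still present is in the Day 0 denominator, adds nothing to the Day 0 numerator, and is censored at month 6. Later risk sets cannot put back an event missing from Day 0.

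The error runs one way only, towards a lower CPE rate and so towards meeting the goal. It concerns a harm of the ablation itself, in a single-arm post-approval study whose purpose includes reporting long-term safety. The SAP's expectation that Kaplan-Meier keeps the impact of missing data small does not carry over to this component.

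**Working it through.** **Inputs from the SAP.** Performance goal 14.8%, assumed CPE rate 6%, one-sided 0.025, power 90%, N = 141 for safety (3.2.2.4); attrition 10% per year and 370 mITT subjects (4.1).

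**Assumptions, not in the SAP.** The true persistent PNI rate q; the share L of those subjects lost before month 12, where it differs from 10%; and the rate o of other CPEs, set at 4% in the main simulation.

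**1. The SAP's own figures.** Power of the one-sample z-test with continuity adjustment is

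Φ{[√n·|p0 − p1| − 1.96·√(p0(1 − p0)) − 0.5/√n] / √(p1(1 − p1))}.

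With n = 141, p0 = 0.148, p1 = 0.06: (1.045 − 0.696 − 0.042)/0.2375 = 1.292, so power is 90.2%. The 141 reproduces. For attrition, 270/0.9³ = 370.4, which confirms that the SAP means 10% lost in each year, so L = 10% in year 1.

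**2. Size of the bias under onset dating.** Only q(1 − L) is recorded at Day 0 instead of q. The PNI component is short by q × L, and the 12-month CPE rate by q × L × (1 − o).

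| Loss before month 12 among affected subjects | q = 1% | q = 2% | q = 4% |
|---|---|---|---|
| 10% (SAP attrition) | 0.10 points (0.4 of 370) | 0.20 (0.7) | 0.40 (1.5) |
| 19% (doubled loss rate, 1 − 0.9²) | 0.19 (0.7) | 0.38 (1.4) | 0.76 (2.8) |
| 30% | 0.30 (1.1) | 0.60 (2.2) | 1.20 (4.4) |

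Entries are q × L in percentage points, with 370 × q × L subjects in brackets.

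**3. Simulation check** (N = 370, 10% loss per year, o = 4%). The Kaplan-Meier 12-month rate as written was 4.90%, 5.79% and 7.44% for q = 1%, 2% and 4%. Counting palsy unresolved at exit gave 5.00%, 5.98% and 7.82%. The differences of 0.10, 0.19 and 0.38 points match q × L × 0.96. With doubled loss among affected subjects they were 0.17, 0.37 and 0.72 points.

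**4. Dependence on the dating rule.** At q = 2%, dating persistent PNI at day 365 with non-informative loss gave 5.98%, the same as counting unresolved-at-exit cases. The bias comes from combining onset dating with a 12-month criterion.

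**5. Effect on the conclusion at the assumed rate.** Using the log-log upper bound for x CPEs in 370 subjects, without censoring:

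- x = 22 (about 6%): 8.9%
- x = 24: 9.5%
- x = 26: 10.1%
- x = 41: 14.7%, still below the goal
- x = 42: 15.0%, above the goal

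The margin is 41 − 22 = 19 subjects, against 0.4 to 1.5 missed at 10% loss.

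**6. Effect at the boundary.** If the true CPE rate were 14.8%, the adjusted z-test at N = 370 passes with up to 40 CPEs, and its exact type I error is 1.6%. A downward bias of 0.1, 0.2, 0.3 or 0.5 points raises this to 1.8%, 2.0%, 2.3% or 2.9%. The log-log bound allows 41 CPEs, so these figures are approximate for the planned analysis.

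**The case against.** **The SAP does not call these subjects event-free.** A reader might infer that the plan scores them as free of CPE. No section says so: they are censored, and the committee decides CPE status and onset. Nothing bars it from classing a palsy unresolved at last contact as a CPE, and a charter or protocol not at hand may say how. That stands as a limit on the claim. But the definition the committee is given requires non-resolution at 12 months, and applying it literally produces the bias.

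**The bias depends on dating.** This also stands. A literal reading of the late-visit rule might date a PNI confirmed after day 365 at day 365, while one confirmed on time is dated at onset. The rule covers late visits only, so it does not help a subject with no 12-month visit. It is a further reason to fix the dating in the text.

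**Table 1 is broken in the text at hand.** It shows seven labels and eight intervals, so the onset interval for persistent PNI cannot be read reliably. Nothing here rests on it; the notes below the table suffice.

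**A sensitivity analysis already exists.** The tipping-point analysis names the safety endpoint and converts the earliest exits first, which probes pass or fail more severely than recoding a few palsies. With 22 CPEs observed, about 20 conversions (42 − 22, ignoring small changes in the risk set) would be needed, out of about 37 subjects lost in year 1. So it partly answers the concern. It is not specific to PNI, leaves the primary estimate as it is, and counts as missing anyone with under 3 years of follow-up, although this endpoint closes at 12 months.

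**Counting every palsy unresolved at exit overcounts.** Some would have resolved. The simulation contained only truly persistent cases, so it does not measure this; each such subject adds 1/370 = 0.27 points. The goal is also tied to the pivotal trial, and the SAP does not say how that trial scored such cases. Both points argue for showing two estimates.

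**Conclusion.** The point holds in a limited form. The 12-month persistence criterion, onset dating and censoring at last contact together leave out palsies unresolved at an early exit and bias the primary CPE rate downward. At the SAP's 10% attrition and assumed persistent PNI rates of 1% to 4%, the bias is about 0.1 to 0.4 points, or 0.4 to 1.5 of 370 subjects. It reaches about 0.2 to 0.8 points if affected subjects leave at twice the rate. Only the 10% comes from the SAP; the PNI rates and differential loss are assumptions.

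A reader might go further and infer that the safety conclusion is unsafe. The figures do not support that: at the assumed 6% rate the upper bound is near 9% against a goal of 14.8%. The bias would matter to pass or fail only if the true rate lay close to the goal. What is affected is the accuracy of the reported rate and the prespecification of one endpoint component. This is a cheap improvement that should be made, not a flaw that undermines the study.

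**What to change.** 1. **SAP 3.2.2.2 and 3.2.2.3:** state that PNI unresolved at the last available assessment, in a subject with no 12-month assessment, counts as a CPE at its onset date. Give the adjudication committee the same instruction.
2. **Reporting:** give the number of such subjects, and show alongside the primary estimate the one that uses only PNI confirmed unresolved at 12 months. The first treats every unknown case as persistent and the second treats none as persistent, so on this component the two bracket the truth.
3. **SAP 3.1.4.2:** for the safety endpoint, define missing data as less than 12 months of follow-up, so that the tipping-point or worst-case analysis matches the endpoint.

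**Cost.** A few sentences and one extra estimate from data already collected. The reported CPE rate may rise by a few tenths of a point because some counted cases would have resolved. It is also a late change to a primary endpoint component, in a SAP already at version 2.0, so the confirmed-only estimate should be reported with equal visibility.
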